- The patients will be randomized into the traditional vs. oral treatment groups (see below for details and protocol). The protocol for each group will be placed in sealed envelopes, 65 for each group, and picked randomly for each patient.
- The patients will attend their normal preoperative visits with the surgical team as well as their regularly scheduled preoperative clearance visit with the medical doctor (Surgery Welcome Center)
- Standard preoperative labs will be obtained (hematocrit, basic metabolic panel), at their preoperative appointment
- Additional preoperative labs will include urine specific gravity to monitor patient hydration which will be obtained the morning of surgery; this will be paid for by the CJR research fund.
- Standard laboratory values (hematocrit and basic metabolic panel) will be obtained postoperative day #1 and #2, if the patient has not been discharged.
- Urine output will be monitored on postoperative day #1 and #2 which is standard protocol
- Additional test will include urine specific gravity on postoperative day #1 and #2 as a marker of hydration as long as the patient is still in the hospital. If the patient is discharged postoperative day #1 we will collect this once in the morning, and once more before they are discharged. Payment of the cost of these laboratory evaluations will come from CJR research funds.
- Patients are encouraged to attend physical therapy 2-3 times a week for 6 weeks. Physical therapy log is attached with ROM and Girth measurement collected once a week for 4 weeks.
- Hematocrit, basic metabolic panel and urine specific gravity 2 weeks postoperatively at their routine follow-up visit will also be obtained. The cost of these laboratory tests will come from CJR research funding.
- Sixty-five patients in each group will be recruited for this study (see stats for power analysis). We will increase our number of enrollment to 75 in each group to account for patients that drop out and withdrawals from the study.

Traditional Fluid Protocol

- NPO Clears and Food after midnight.
- 2 Liters of lactated ringers administered by anesthesia intraoperatively.
- Postoperatively - 2 Liters of Crystalloid while in PACU and Inpatient Room for a Total of 4 Liters of Crystalloid within 24 hours.
 - Patient will receive 500 milliliters while in PACU and 1500 milliliters while in their Inpatient Room, for a total of 2 Liters.

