- Spinal drug choice standardized: 9 mg (1.2 ml) –11.25 mg (1.5ml) of Spinal Bupivacaine 0.75%with Dextrose 8.25%. We have also attached the spinal anesthesia guidelines that will be followed for this study (see attached).
- Ondansetron 4mg IV given prior to regional anesthesia; repeat x 1 prior to the end of surgery.
- Ultrasound Guided Adductor Canal Block using 30 ml of Ropivacaine 0.35% Preservative Free.
- Normal diet postoperatively.

Oral Fluid Protocol

- Patients encouraged to drink a minimum of three, 20 ounce cups of clear liquid per day each day for the 3 days prior to procedure. Examples of clear liquids include water, clear sports drinks, fruit juices without pulp. Please limit caffeinated and carbonated beverages to no more than 1 drink per day.
- NPO Food/Milk: none beginning 8 hours prior to procedure time.
- NPO Clear Liquids — Patients are asked to drink 10 ounces of clear liquid 4 hours prior to their scheduled procedure time.
- In the preoperative holding area, an IV is started in the patient; and the patient is given Lactated Ringers IV fluid at a rate of 75ml/hr. The IV fluids will be stopped and the IV hep-locked in the PACU when the patient is taking PO fluid; the total amount of IV fluids given to the patient is charted and is not to exceed 500ml total.
- Spinal drug choice standardized: 9mg (1.2 ml) -11.25(1.5ml) mg of Spinal Bupivacaine 0.75%with Dextrose 8.25%.
- Ondansetron 4mg IV given prior to regional anesthesia; repeat x 1 prior to the end of surgery
- Ultrasound Guided Adductor Canal Block using 30 ml of Ropivacaine 0.35% Preservative Free. Normal diet postoperatively.
- PO fluid protocol implemented on the floor immediately postop: a minimum of three, 20 ounces cups of liquid per day for 3 days. Patients can drink more than the minimum if they feel dehydrated.

Primary Outcomes

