A. Body Weight – scales will be purchased and provided to the patient while participating in the study. All weights will be obtained on the same scale for each patient to assure consistency of measurements. Measurements will be performed in the preoperative holding area prior to surgery, the evening of surgery on the orthopaedic floor and every morning the patient is hospitalized using the same scale assigned to that patient. Body weight measurements will be repeated at home 48 hours' post-discharge and at one and two weeks either at home or in the clinic with the same scale as previously utilized. An additional measurement will be obtained at 3 weeks postoperatively if the patient's body weight at 2 weeks has changed more than +/- 2% from their preoperative value. Funding of the cost of the scales will come out of the CJR research funding.

B. Knee Range of Motion: This will be assessed preoperatively (at their clinic appointment), on POD #1 and 2 by the research staff if the patient has not been discharged, and at 1, 2, 3 and 4 weeks postoperatively by the outpatient physical therapy office. Patient standardized forms will be provided to the outpatient physical therapists to record all post-hospital measurements. Measurements will be done with a standard goniometer.

C. Leg Anthropometric (Girth) Measurements: girth measurements will be performed at 5 & 10 cm suprapatellar, midpatella, and 10 cm infrapatellar with the use of a standard tape measure. These measurements will be collected at their pre-operative visit by research staff, POD 1 and 2 by research staff, if the patient has not been discharged and post-discharge measurements will be performed by the outpatient physical therapist at the same intervals and recorded on the same outpatient data sheet as described in item B above.

D. Transfusion: Number of transfusions will be recorded and compared between both groups. Transfusion criteria will not deviate from our normal post-operative care protocol.

E. Wound Complications: the incidence of wound infection and wound drainage will be assessed and recorded. Compressive dressings will be changed daily until wound is dry. If wound is draining at hospital discharge, the patient will be provided with home dressing supplies and instructed on how to perform daily dressing changes. The patient will take a daily photo of the wound and removed dressing daily and email it to CJR until the wound is dry. This is standard protocol for our patients currently.

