Based on my reading of the fluid management protocol, the study evaluates the hypothesis that the euvoolemia regimen leads to better outcomes than the traditional regimen. The former corresponds to the treatment group and the latter to the control group for the analysis, and assuming that the two groups demonstrate similarities in terms of potential pre-treatment confounding variables, such as measures obtained from preoperative history and physical, a comparison of post-treatment outcomes seems appropriate (e.g., t-tests). Even under random assignment to treatment, checks can be performed to ensure effective equivalence of confounders across treatment and control groups, an essential step in the case of small samples. If the results of such checks reveal potential confounding, including control variables in the analysis may be appropriate (e.g., in a linear regression) or a matching design to generate treatment-control pairs can be used.

While I do not have any substantive training in this field, it seems that some of the outcomes listed in the Procedures: Primary Outcomes section of the protocol may be mediated by others. For example, the association between receiving the treatment and readmission or length of hospitalization may be mediated by some of the other outcomes listed. Are there any known or suspected mediators at this point, either from the list of outcomes or beyond?

Concerning statistical power, in the figure below I calculate power (y-axis) for a range of hypothesised values of estimated effect sizes (colored lines), sample sizes per treatment and control group (x-axis), and arbitrarily chosen levels of significance (α) across the panels. Regarding α , I start with 0.05 and then make an adjustment based on an arbitrary number of hypotheses to be evaluated (eight, in this demonstration). The solid horizontal line at 0.8 represents the commonly accepted power value. As an example from Figure 1(b), for a medium-high effect size of 0.6 (green line) and evaluating eight hypotheses, in order to achieve power of 0.8 would require approximately 65 participants in each of the treatment and control groups.

[figure not shown]

Figure 1: Power calculations for hypothetical effect sizes and sample sizes (per group) at given values of α . The left panel uses $\alpha = 0.05$ and the right panel employs a Bonferroni correction for multiple hypotheses. In this case, evaluating eight hypotheses with a desired α of 0.05 yields an adjusted α of 0.00625.

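### In-hospital body weight, listed as a primary outcome, is partly a measure of the assigned IV volume, and a difference in it does not by itself show better outcomes

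*Combined protocol and SAP*

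**What the plan says.** Body weight is item A of the 20 lettered items (A to T) under Primary Outcomes in Section 2. It is measured in the holding area before surgery, then "the evening of surgery on the orthopaedic floor and every morning the patient is hospitalized", and is "repeated at home 48 hours' post-discharge and at one and two weeks either at home or in the clinic". A week-3 weight is added only if the two-week value differs from the preoperative value by more than 2% in either direction. No primary time point, summary measure (raw weight or change) or direction of benefit is given.

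The arms are defined by fluid:

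- **Traditional Fluid Protocol:** 2 L during surgery and 2 L afterwards, "for a Total of 4 Liters of Crystalloid within 24 hours". The postoperative part is split: "Patient will receive 500 milliliters while in PACU and 1500 milliliters while in their Inpatient Room".
- **Oral Fluid Protocol:** "the total amount of IV fluids given to the patient is charted and is not to exceed 500ml total". On the floor these patients also drink "a minimum of three, 20 ounces cups of liquid per day for 3 days".

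Section 9 states the hypothesis that the new regimen "leads to better outcomes than the traditional regimen" and suggests t-tests of post-treatment outcomes. It uses eight hypotheses as an illustrative number and does not name them.

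**The concern.** A primary outcome should be something the treatment may or may not change. In-hospital weight is close to the treatment itself: a litre of infused crystalloid weighs about 1 kg, and the weighing takes place while that fluid is being given or soon after. The evening weight also falls at an unspecified point in the 1.5 L given in the inpatient room, so its relation to the assigned volume varies between patients.

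The risk lies in interpretation. A lower in-hospital weight in the Oral arm could be reported as a primary result supporting the Section 9 hypothesis even if motion, wounds, function, length of stay and readmission did not differ. Nothing in the plan prevents this, because the hypotheses are not listed and weight has no stated role.

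**Working it through.** **1. The plan's own figure.** Section 9 gives about 65 per group for effect size 0.6, power 0.8 and alpha 0.05/8 = 0.00625. By noncentral t, a two-sided test has power 0.738 at 65 per group and needs 73. A one-sided test has power 0.811 and needs 64. The figure is reproduced only as one-sided, and the plan does not state sidedness. This point does not depend on that. Two-sided alpha 0.00625 and 65 per group are used below.

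**2. The assigned IV gap (Section 2).**

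- By the end of PACU: 2.0 + 0.5 = 2.5 L against at most 0.5 L, so at least 2.0 L.
- By 24 hours: 4.0 − 0.5 = at least 3.5 L.

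The gap rests on the 4 L in the Traditional Fluid Protocol. Section 1 instead describes an unspecified intraoperative amount and then a set floor rate. The two descriptions must be reconciled.

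**3. Oral intake.** The Oral arm's floor minimum is 3 × 20 = 60 oz per day, and 60 × 0.02957 = 1.77 L. The Traditional arm has a normal diet with no stated volume. In the severe case where the Traditional arm drinks nothing, the 24-hour gap becomes 3.5 − 1.77 = 1.73 L before any urine loss.

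**4. Power on change from the holding-area weight.** Net difference = retained share × gap × 1 kg/L; d = net difference / SD; noncentrality = d × √(65/2); 128 df. The documents give neither the retained share nor the SD of change, so both are assumed and varied.

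| Net difference | SD 1 kg | SD 1.5 kg | SD 2 kg | SD 3 kg |
|---|---|---|---|---|
| 1.75 kg (50% of 3.5 L) | >99.9% | >99.9% | 98.5% | 70.6% |
| 1.0 kg (50% of 2.0 L) | 99.8% | 84.4% | 53.0% | 19.4% |
| 0.875 kg (25% of 3.5 L) | 98.5% | 70.6% | 39.1% | 13.7% |
| 0.86 kg (50% of 1.73 L) | 98.3% | 69.0% | 37.8% | 13.2% |

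Power of 80% needs d = 0.637. At SD 1, 2 and 3 kg that is 0.64, 1.27 and 1.91 kg, or 18%, 36% and 55% of 3.5 kg.

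**5. Power on raw post-operative weight.** Section 9 read literally compares post-treatment values. With assumed between-patient SDs of 12, 15 and 18 kg, even the full 3.5 kg gives power of 14%, 8% and 5%.

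**6. The baseline.** The Oral arm is asked to drink 10 oz (10 × 0.02957 = 0.30 L) four hours before the procedure, while the Traditional arm takes no clear fluids after midnight. The holding-area weight therefore already follows part of the assigned regimen. It may be raised in the Oral arm, which would enlarge the apparent gain in the Traditional arm.

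**The case against.** The strongest reply is that weight is a legitimate physiologic outcome. Sections 1, 3 and 4 name physiologic measures as primary, and Section 1 gives fluid overload as a route to complications. Retained fluid also depends on urine output, losses and drinking, so it is not identical to the volume infused. This stands: in-hospital weight is a mechanistic marker and should be measured. But the plan does not show that a smaller early gain means fewer complications, and it records wounds, stay and readmission directly (items E and I).

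A reader might go further and infer that a significant result favouring Oral is all but certain, or that early weight carries no information about benefit. The documents support neither. Power depends on retention, SD and Traditional drinking, none of which is stated, and on a change-from-baseline analysis that the plan does not specify. No direction of benefit is defined for weight. The stated harm pathway gives weight some meaning.

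Nor should the 2% figure be read as the plan's threshold for a notable early change, since it only triggers an extra weighing after week 2.

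It is also fair to say that the wider problem is 20 primary items with no named hypotheses. Settling that list could settle the role of weight, but the list would still have to state that role.

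**Conclusion.** The point holds in a limited form. Evening-of-surgery and in-hospital weights are partly driven by an assigned IV gap of at least 2.0 L by the end of PACU and 3.5 L by 24 hours, and so cannot alone support a claim of better outcomes. That conclusion needs no assumption about power, though the gap rests on the volumes in the two fluid protocols.

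How easily the comparison reaches significance does depend on assumptions. It is likely on change from the holding-area weight if about half the 24-hour gap is retained and the SD of change is about 2 kg or less. It is not assured with lower retention, a larger SD or a strong oral offset, and it is unlikely on raw weights. The same listed outcome can thus be easily reached or almost uninformative, depending on an analysis choice that the plan leaves open.

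The point does not extend to the weights at 48 hours after discharge, one week and two weeks.

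**What to change.** Change the wording of item A and Section 9, and collect everything as now:

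- Classify evening-of-surgery and in-hospital weight as a treatment-separation and mechanistic measure, outside the hypotheses used to claim better outcomes.
- Analyse it as change from, or adjusted for, the holding-area weight. Report that weight by arm, because it follows the assigned preoperative drinking.
- Keep the weights at 48 hours after discharge, one week and two weeks as physiologic outcomes.
- State that a weight difference alone will not support a conclusion of better outcomes.
- Reconcile the Section 1 description of the Traditional regimen with the volumes in the Traditional Fluid Protocol.

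This needs no new data or patients. The trial gives up one potentially easy primary result.

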F. Thromboembolic Disease: Screening will be based on clinical assessment of the participating medical team members, which is standard protocol with all of our patients. The incidence of thromboembolic events will be recorded. All patients in the study will use aspirin 81 mg twice daily for DVT prophylaxis.

G. Muscle Strength: quadriceps strength will be assessed on POD #1 and 2 by research staff (in the hospital) and repeated at 2 and 6 weeks postoperatively at their standard of care follow-ups in the office by research staff. The strength testing will be calculated using a handheld dynamometer which is standard testing for strength in many post-operative patients currently.

H. Functional Performance Assessment: Functional tests will be performed at their preoperative appointment and once again at their 2 and 6 weeks postoperatively and will include the timed up and go (TUG) and the 30 second sit-to-stand tests. The tests will be performed in the office by research staff. These are standard tests that are often performed in physical therapy clinics to assess patient progress.

I. Length of the Hospitalization & Readmission Incidence will be recorded for both groups.

J. Postoperative Pain Assessment: Pain will be assessed using a pain VAS scale daily while hospitalized, then three times per day for 4 weeks postoperatively. Patients will be given a log to record these measurements outside of the hospital setting.

K. Adverse Events: episodes such as symptomatic hypotension (light-headedness, syncope), emesis, the need the IV fluid boluses, and other hospital and post-discharge events will be recorded.

L. Blood Pressure: this will be recorded in the Preoperative Care Unit, PACU, upon arrival to the nursing unit, and every 8 hours thereafter while hospitalized. This is standard practice for all of our patients currently.

M. PONV (Post-operative Nausea and Vomiting) - PONV will be assessed throughout their hospital stay; vital signs are checked per hospital nursing protocol, patients will be asked about Nausea: None, Mild, Moderate or Severe.

N. Patient Reported Outcome – We will be collecting the Knee Society Score(KSS) Knee injury and Osteoarthritis Outcome Score (KOOS) and the VR-12 from the patients pre-operatively as well as at their 2 week and 6 week follow up appointments. These are validated patient reported outcome measures that are already collected as standard of care at Colorado Joint Replacement.

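### The one body weight between hospital and week 1 is timed from discharge, so its postoperative day depends on length of stay, itself a listed outcome

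*Combined protocol and SAP*

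**What the plan says.** Section 2, Primary Outcomes, item A sets the weight schedule. After a weight in the preoperative holding area, weights follow on "the evening of surgery on the orthopaedic floor and every morning the patient is hospitalized". The next reading is set by discharge: "Body weight measurements will be repeated at home 48 hours' post-discharge". Later weights come "and at one and two weeks either at home or in the clinic with the same scale as previously utilized", without saying whether the weeks count from surgery or from discharge. A further weight, conditional on the two-week value, is explicitly timed at three weeks after surgery.

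Item J, on pain, reads "Pain will be assessed using a pain VAS scale daily while hospitalized, then three times per day for 4 weeks postoperatively". It adds "Patients will be given a log to record these measurements outside of the hospital setting", which places the change in frequency at discharge.

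Item I, under the same Primary Outcomes heading, reads "Length of the Hospitalization & Readmission Incidence will be recorded for both groups". Section 2 has a special rule for patients discharged on POD 1 and makes POD 2 measurements conditional on still being in hospital, so stay is expected to vary. Sections 1 and 3 cite abdominal-surgery trials suggesting that large fluid volumes may lengthen stay.

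Section 9 gives t-tests as an example of the between-group comparison, with regression or matching if baseline checks show confounding. It names no analysis day, visit window or pain summary.

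**The concern.** Randomization makes the arms comparable at a given time after surgery. It does not make them comparable at a time set by something that happens after randomization and that treatment may influence. The 48-hour weight is such a reading. If one regimen shortens stay, that arm is weighed on an earlier postoperative day. If weight is still changing then, the arms differ at this reading even when the regimens have the same effect on weight at every postoperative day.

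Nothing in section 9 repairs this. The adjustment it describes is for pre-treatment variables, and adding length of stay as a covariate would condition on an outcome. Most other serial measures in section 2 are counted from surgery: motion and girth on POD 1 and 2 and then by week, strength and function at 2 and 6 weeks. The 48-hour weight departs from that pattern.

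Pain raises a milder form of the same issue. The number of scores on a given early day depends on whether the patient is still in hospital.

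**Working it through.** The plan states no figure on this point, so there is none to reproduce. The check is a count of the schedule followed by illustrations with assumed values.

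**1. Schedule by discharge day.** Inputs: items A and J. Assumptions: discharge follows the morning weight, and three-times-daily scoring starts the next day. With discharge on POD D, weights fall on POD 0, on mornings 1 to D, and on POD D + 2.

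| Discharge | Weights on POD | Pain scores, POD 1–3 | Pain scores, POD 1–28 |
|---|---|---|---|
| POD 1 | 0, 1, 3 | 1 + 3 + 3 = 7 | 1 + 27 × 3 = 82 |
| POD 2 | 0, 1, 2, 4 | 1 + 1 + 3 = 5 | 2 + 26 × 3 = 80 |
| POD 3 | 0, 1, 2, 3, 5 | 1 + 1 + 1 = 3 | 3 + 25 × 3 = 78 |

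Every patient has POD 0 and POD 1. After that, no day before week 1 is common to all three rows. The 48-hour weight moves one postoperative day for each extra hospital day.

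**2. Weight, if mean stay differs.** Suppose there is no treatment effect on weight and weight changes at a constant *r* kg/day around POD 3 to 5. The mean day of this reading is mean stay + 2, so

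spurious arm difference = *r* × (difference in mean stay).

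The documents give neither input. Assumed ranges:
- 0.3 kg/day × 0.25 day = 0.075 kg
- 0.8 kg/day × 0.5 day = 0.4 kg

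Wider assumptions, 0.2 kg/day × 0.25 day to 1.0 kg/day × 1.0 day, give 0.05 to 1.0 kg. The sign follows from the two inputs: if weight is falling, the arm that stays longer is weighed later and reads lower.

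**3. Weight, if stays do not differ.** There is then no bias between arms. Patients are still weighed on different days, which adds about *r*² × Var(stay) to the variance of the reading. For one patient, a one-day shift is 0.3 to 0.8 kg at the same assumed rates.

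**4. Pain, if all readings are averaged.** Assumed course over POD 0–7: 6, 5.5, 5, 4.5, 4, 3.7, 3.4, 3.1 (sum 35.2, daily mean 35.2/8 = 4.40). Hospital days carry weight 1 and home days weight 3:
- discharge POD 1: (11.5 + 3 × 23.7)/20 = 82.6/20 = 4.13
- discharge POD 2: (16.5 + 3 × 18.7)/18 = 72.6/18 = 4.03
- discharge POD 3: (21 + 3 × 14.2)/16 = 63.6/16 = 3.98

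One extra day of stay shifts the average by 4.13 − 4.03 = 0.10 or 4.03 − 3.98 = 0.05 to 0.06 points. For an arm difference of 0.25 to 0.5 day this is roughly 0.02 to 0.05 points. Over 28 days, with pain assumed to fall linearly from 6 to 2, the averages are 3.95, 3.90 and 3.86 against a daily mean of 4.00. That is about 0.05 per day of stay, or 0.01 to 0.02 points at the same arm difference.

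**The case against.** The best case for the plan is that most of the weight schedule is sound. The planned intravenous contrast, 4 litres within 24 hours against at most 500 ml, falls largely before or around the first hospital morning. The evening-of-surgery and POD 1 weights capture it at common times. Stay is recorded, so the intended day of each 48-hour weight can be recovered. All of this stands. It limits the point to one reading, but that reading still has no common day and no analysis rule.

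Several stronger readings are tempting and are not supported:

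- *All weights after discharge are tied to discharge.* Only one is. Weeks 1 and 2 state no anchor, and the surgery-based wording of the conditional three-week weight suggests they count from surgery.
- *The Oral group will go home earlier, be weighed nearer its peak and have a benefit hidden.* The documents give no stay figures, no weight course and no peak day. The direction is unknown.
- *The 2% trigger is a yardstick for the bias.* It applies to the two-week weight and is not an effect size.
- *The reading falls at the clock hour of discharge, against mornings in hospital.* No clock time is specified for it.
- *The shift moves Oral patients across the end of the postoperative drinking regimen,* "a minimum of three, 20 ounces cups of liquid per day for 3 days". If the day of surgery is day 1, the regimen covers POD 0 to 2, and POD 3 and 4 both lie after it. If POD 1 is day 1, POD 3 lies inside and POD 4 outside. The plan does not say which applies.
- *Pain results are materially distorted.* The plan nowhere says that all readings will be pooled, and setting POD 1 discharge against POD 3 (4.13 against 3.98) uses a two-day gap in stay, larger than the arm difference assumed for weight.

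**Conclusion.** The point holds for one scheduled reading of a listed primary outcome. The 48-hour weight falls on POD 3, 4 or 5 according to stay, and stay may depend on treatment. That much follows from the text.

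Bias between arms needs two further conditions: mean stay differs, and weight is still changing at POD 3 to 5. Under the assumed 0.3 to 0.8 kg/day and 0.25 to 0.5 day it is about 0.08 to 0.4 kg, with direction unknown. If stays do not differ, the cost is added variance alone.

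The pain point is secondary. It arises only if readings are averaged without regard to day, and it then amounts to about 0.02 to 0.05 points over the first week and less over four weeks. The plan's real gap there is an undefined pain summary.

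This should be changed because the change is cheap and a common-day weight cannot be collected afterwards. It does not undermine the early weight comparison or the trial as a whole.

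**What to change.** **Item A.** Replace the 48-hour post-discharge weight with a weight on one fixed postoperative morning for every patient, for example POD 3, in hospital or at home on the assigned scale. State that weeks 1 and 2 count from surgery. On the schedule above, a POD 1 discharge is still weighed at home on POD 3, a POD 2 discharge is weighed one day sooner than now, and a POD 3 discharge already has that morning's hospital weight. No home weighing is added.

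**Item J and section 9.** Define the pain summary as daily means analysed by day since surgery. This removes the pooling problem without any change in collection. Using the three-times-daily log in hospital as well would equalise precision across days, at a cost of two more scores per hospital day.

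**If data are already collected.** Derive the actual postoperative day of each 48-hour weight from the recorded discharge, and analyse weight by time since surgery. Do not compare arms at a nominal 48-hour visit or adjust for length of stay as a covariate. This is weaker than a fixed day because it relies on a model for the weight course between days.

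The cost is wording in items A and J and section 9, and a line in the patient log.

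### After discharge, knee ROM and girth are measured only at encouraged therapy visits in weeks 1-4, with no backup and no week 6 value, although research staff test patients at weeks 2 and 6

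*Combined protocol and SAP*

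**What the plan says.** All references are to the combined protocol and SAP.

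- **Section 2, Primary Outcomes, item B (ROM).** ROM is assessed preoperatively at the clinic appointment, then "on POD #1 and 2 by the research staff if the patient has not been discharged", then "at 1, 2, 3 and 4 weeks postoperatively by the outpatient physical therapy office". On standardisation: "Patient standardized forms will be provided to the outpatient physical therapists to record all post-hospital measurements", and "Measurements will be done with a standard goniometer".
- **Item C (girth).** Four fixed sites are measured with a standard tape. Research staff take the preoperative and in-hospital values, and "post-discharge measurements will be performed by the outpatient physical therapist at the same intervals".
- **Section 2, Procedures (therapy).** "Patients are encouraged to attend physical therapy 2-3 times a week for 6 weeks". The next sentence reads: "Physical therapy log is attached with ROM and Girth measurement collected once a week for 4 weeks".
- **Items G, H, N and Q.** Quadriceps strength is "repeated at 2 and 6 weeks postoperatively at their standard of care follow-ups in the office by research staff". Research staff also run TUG and sit-to-stand in the office at weeks 2 and 6, and office research staff take bioimpedance at those visits. KSS, KOOS and VR-12 are collected at the same two appointments.
- **Section 9, Methods of Evaluation.** Outcomes after treatment are to be compared between arms, for example by t-test. Regression or matching is offered if baseline checks suggest confounding.

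No item gives ROM or girth to research staff after discharge. The protocol text names no substitute reading for a patient who misses therapy or whose form does not come back.

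**The concern.** Two outcomes on the primary list depend, after discharge, on visits that the trial does not require. A patient in more pain, with more swelling or with a slower recovery may attend less. A patient who recovers quickly may also stop going. Either way, the presence of a value can be tied to what the fluid regimens are meant to affect. If attendance then differs by arm, or is related to recovery differently in each arm, a comparison of the available values is no longer protected by randomisation. The t-tests and baseline adjustment in Section 9 do not deal with missingness that arises after randomisation.

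The hospital readings do not fill the gap. They are taken on postoperative days 1 and 2 only while the patient is still an inpatient, and length of stay is itself an outcome (item I).

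The schedule also leaves week 6 empty for ROM and girth. The trial could not say whether an early difference in swelling or motion had gone by then, or whether it accompanied the 6-week results for strength and function.

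**Working it through.** **1. Who measures what, and when, after discharge**

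| Outcome | Assessor | Weeks | Depends on attending therapy? |
|---|---|---|---|
| ROM (B) | outpatient therapy office | 1, 2, 3, 4 | yes |
| Girth (C) | outpatient therapist | 1, 2, 3, 4 | yes |
| Quadriceps strength (G) | research staff, office | 2, 6 | no |
| TUG, sit-to-stand (H) | research staff, office | 2, 6 | no |
| KSS, KOOS, VR-12 (N) | collected at follow-up appointments | 2, 6 | no |
| Bioimpedance (Q) | research staff, office | 2, 6 | no |

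ROM and girth are the only rows that rely on therapy attendance, and the only ones without a week 6 value. Staff who could take the readings already test the patient at weeks 2 and 6.

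**2. The plan's own sample size**

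Inputs from Section 9: standardised effect 0.6, power 0.8, α = 0.05/8 = 0.00625. Sidedness is not stated. A two-sample t-test needs 64 per group one-sided (power 0.811 at 65), which agrees with the plan's approximate 65. Two-sided it needs 73 (power 0.738 at 65). Both versions are carried below.

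**3. The allowance for loss**

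Section 2 raises enrolment from 65 to 75 per group: 1 − 65/75 = 13.3%. The stated reason is dropout and withdrawal. Missed therapy readings are not mentioned.

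**4. Loss of precision if logs are missing**

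The documents give no attendance or form-return rate, so 10-30% missing is an assumption. With fraction m missing in each arm, the standard error is multiplied by √(1/(1 − m)):

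- m = 0.10: √(1/0.9) = 1.054, a rise of about 5%
- m = 0.30: √(1/0.7) = 1.195, a rise of about 20%

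Power at effect 0.6 and α = 0.00625, shown as one-sided / two-sided:

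| Missing | From 75 per group | Power | From 65 per group | Power |
|---|---|---|---|---|
| 0% | 75 | 0.87 / 0.81 | 65 | 0.81 / 0.74 |
| 10% | 67.5 | 0.83 / 0.76 | 58.5 | 0.76 / 0.68 |
| 20% | 60 | 0.77 / 0.69 | 52 | 0.70 / 0.61 |
| 30% | 52.5 | 0.70 / 0.61 | 45.5 | 0.62 / 0.53 |

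The left half applies if nobody drops out and the whole allowance is free to absorb missing logs. The right half applies if dropout and withdrawal use up the allowance first. Keeping 65 evaluable per group against missing logs alone would need 65/(1 − m), rounded up: 73, 82 and 93 enrolled at 10%, 20% and 30%.

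These figures cover precision only. The documents do not allow the size or direction of any bias from selective attendance to be estimated.

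**The case against.** **The change of rater.** A reader might infer that moving from clinic or hospital assessors to therapists mixes a rater effect with the treatment effect. The documents do not support that. The same rule applies in both randomised arms, and Section 9 plans a comparison of outcomes after treatment. A change of rater adds noise; it biases the contrast only if raters or attendance differ by arm. The standardised forms, standard goniometer and tape, and fixed girth sites limit part of that noise, although no therapist training is described.

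**A smaller effect size.** A reader might also calculate that rater noise shrinks the planned 0.60. With an assumed patient SD of 10 degrees, 0.60 is 6 degrees. Adding an assumed between-rater SD of 3-7 degrees gives 6/√(100 + 9) = 0.57 to 6/√(100 + 49) = 0.49. Both SDs are assumed, the sum credits research staff with no rater variation, and 0.6 is a worked example in Section 9 that is not tied to ROM. The shrinkage is not part of this point.

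**Who takes preoperative ROM.** Item C names research staff for preoperative girth. Item B gives only the clinic appointment, and its mention of research staff may cover just postoperative days 1 and 2. It should not be stated as fact that research staff take the baseline ROM.

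**The week 4 stop.** Ending at week 4 is a legitimate choice in itself. The pain log also ends there (item J), and body weight ends at week 2, or week 3 under a condition (item A). No stated aim links swelling or motion to 6-week function, and at week 2 all these measures are scheduled together. This weakens the week 6 argument but does not remove it, since patient function is a declared primary interest (Section 4) and is read at week 6.

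**Attendance and forms.** With two or three sessions encouraged each week, one weekly reading does not need full attendance. The Physical Therapy Log is an attachment not reproduced here, and it may carry instructions on measurement or return. Non-return is therefore a risk and not an established fact.

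**Conclusion.** The point holds as a weakness of design that should be corrected. ROM and girth, both on the primary list, have no source after discharge other than therapy visits that patients are merely encouraged to attend. The protocol text gives no fallback, and the analysis plan does not address missingness related to recovery. There is also no week 6 value to set beside strength, function, patient-reported outcomes and bioimpedance.

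The size is illustrative. If 10-30% of logs are missing, the standard error rises by about 5-20%. If the enrolment allowance is not otherwise used, power at effect 0.6 falls from 0.87 to 0.83-0.70 one-sided, or from 0.81 to 0.76-0.61 two-sided. This assumes equal loss in both arms and no bias; any selective attendance would add to it. The point does not claim that the rater change confounds the comparison or that logs will in fact be missing.

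**What to change.** - In items B and C, add ROM and the four girth sites to the existing week 2 and week 6 office visits, measured by research staff with the technique used at baseline.
- State in Section 9 that these values enter the between-arm comparison.
- Keep the weekly therapist readings for weeks 1-4 in the analysis as planned. Reducing them to description would give up most of the early course, which matters for a perioperative intervention.

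The cost is a few minutes with a goniometer and tape at two visits that already take place, one added form line and a protocol amendment. No new visit or staff are needed. One limit remains: the documents state no blinding of research staff, so the change secures availability and a common group of assessors but does not by itself remove assessor bias.
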